#### **5.6.3.1.2 Urinalysis parameters**

The following parameters are measured:

- Urinalysis: pH, bilirubin, glucose, ketones, urobilinogen, protein, nitrite
- Urine Sediment: albumin, bacteria, crystals, RBC, WBC

The number and percentage of participants with each response category for qualitative urinalysis and urine sediment parameters are summarized for the scheduled time points. Percentages are relative to the number of participants with a result for each parameter at each time point.

Shift from Baseline to the post-Baseline time point (Day 3, Day 11) for observed values (negative, trace, 1+, 2+, 3+, etc) is summarized for the above qualitative urinalysis parameters (bilirubin, glucose, ketones, urobilinogen, protein, nitrite).

#### **5.6.3.1.3 Pregnancy test**

Results of serum and urine pregnancy tests are not summarized but are provided in a subject data listing.

#### **5.6.3.2 Vital Signs**

The following parameters are measured:

- systolic blood pressure (SBP), diastolic blood pressure (DBP), pulse rate, respiratory rate, and body temperature.

Observed values for the vital sign parameters are summarized with descriptive statistics for the scheduled time points. Changes from Baseline (Day1-predose) for each parameter are summarized for all post-Baseline time points.

#### **5.6.3.3 Electrocardiograms**

12-lead ECG will be recorded 3 times at 15min [ $\pm 5\text{min}$ ] intervals within 24h before dosing of BRY on Day 1 in order to get representative Baseline. Postdose 12-lead ECG will be recorded 1 time. The individual mean at Baseline will be calculated as raw parameters for descriptive analysis. The definition of Baseline will be the mean of the triplicate measurements predose on Day 1 or Day -1. If there are less than three replicates at Day 1 or Day -1 predose, the mean of the available replicates (predose) will be taken as Baseline.

The following parameters are measured:

- Heart rate, RR interval, PR interval, QRS interval, QT, QTcB\*, QTcF\*\*

\* QT interval corrected for heart rate by Bazett's formula

\*\* QT interval corrected for heart rate by Fridericia's formula

Observed values for the ECG parameters are summarized with descriptive statistics for the scheduled time points. Changes from Baseline for each parameter are summarized for all post-Baseline time points.

For QTcB and QTcF, observed values and their changes from Baseline are summarized based on the classifications of [ $<450$ ,  $450-480$ ,  $480-500$ ,  $\geq 500$  msec] and [ $<30$ ,  $30-60$ ,  $\geq 60$  msec], respectively.

The individual measurements and the mean of the triplicate measurements will be reported in the by-participant listings. The listing will also include the change from Baseline. All ECG findings for the individual measurements will be listed separately.

#### **5.6.3.4 Other safety endpoint(s)**

##### **Physical examination**

Participants with abnormalities in the physical examination will be listed including details of the abnormality.

##### **Suicidal risk monitoring**

Columbia-Suicide Severity Rating Scale (C-SSRS; Posner et al, 2011) data where ideation or suicidal behavior had been reported will be listed. Module of the questionnaire, time point, question and the associated response will be listed.

### **5.7 Other Analyses**

#### **5.7.1 Other endpoints and/or parameters**

##### **5.7.1.1 Pharmacokinetics**

In general, plasma concentration-time profiles of BRV and its metabolites are summarized by dosing period (single and multiple dose) using PK-PPS and listed by subject for the SS. PK parameters of BRV and its metabolites are summarized by dosing period (single and multiple dose) using the PK-PPS and listed by subject for the SS.

Descriptive statistics for plasma concentrations of BRV and its metabolites are provided for every scheduled time point (see [Table 1](#)– and [Table 1–3: Multiple-Dose Period: schedule for ECGs, vital signs, and PK sampling](#) 3) by dosing period.

Descriptive statistics include the number of values (n), arithmetic mean, SD, geometric mean, lower and upper limit of the 95% CI for geometric mean, geometric CV [%], median, minimum and maximum values.

Concentrations BLQ are replaced by half of the LLOQ and missing values are excluded for the calculation of descriptive statistics. When the mean includes one or more replaced BLQ values, a

footnote of the table should be added "contains one or more BLQ values replaced by half the LLOQ value". For each specific time point, only minimum and maximum should be calculated in case the number of BLQ and missing values exceed one third of the total; other descriptive statistics should be reported as missing ("--"). If minimum and/or maximum is BLQ, keep minimum or maximum as "BLQ". A minimum of 3 values are required to calculate summary statistics; if only 2 values are available then these should be presented as the minimum and maximum with other descriptive statistics reported as missing ("--").

Listings for individual concentrations of BRV and its metabolites including the actual and nominal sampling times and the deviation between the actual and nominal sampling times are provided. Concentrations that are BLQ are indicated as "BLQ" in the listings. Missing data should be reported as "NV" (no value). Concentrations should be listed to the same number of significant figures supplied by the bioanalytical laboratory.

Geometric mean profiles vs nominal time are displayed (including corresponding lower and upper limit of 95% CI for the linear scale, without CI on the semi-logarithmic scale) superimposing in one plot for all analytes, with one plot for each dosing period. Summary data plotted in the figure will match data presented in summary table, except for missing values prior to  $C_{max}$  which will be set to 0 in the figure.

Individual concentration-time profiles vs scheduled time are displayed graphically on a linear scale and semi-logarithmic scale, superimposing in one plot all analytes, and one plot per dosing period and per participant. A Spaghetti plot of individual plasma concentrations vs scheduled time is displayed by dose period. When reporting individual data in figures, BLQ values prior to  $C_{max}$  will be set to 0 and BLQ values that occur post- $C_{max}$  will be considered missing.

### **Primary/secondary pharmacokinetic parameters**

Plasma pharmacokinetic parameters as identified above are calculated from the individual drug concentration vs. actual time profiles by dosing period. Parameters are calculated for BRV and metabolites after single and multiple dose as described in **Table 5-4**.  
**Table 5-4:**

#### **Primary/Secondary pharmacokinetic parameters**

Pre-dose sample time is set to 0 prior to performing parameter derivation. Missing pre-dose concentrations for Single-Dose period will be replaced by 0. For multiple dose period, the analyst should use scientific judgement to assess what action should be taken and a rationale for this action should be recorded in the analysis documentation (eg set to 0 if no accumulation is expected).

**Table 5-4: Primary/Secondary pharmacokinetic parameters**

Specimen	PK Parameter		BRV		Metabolites a	
	Notation	Description	Single	Mult.	Single	Mult.
Plasma	AUC (0-t)	area under the plasma concentration-time curve from zero to the time of the last measured concentration above the LOQ	P	—	S	—
	AUC (0-12),ss	area under the curve from 0 to 12 hours at steady state	—	P	—	S

	AUC	area under the curve from 0 to infinite time	S	-	S	-
	C max	maximum plasma concentration	P	-	S	-
	C max,ss	maximum plasma concentration at steady state	-	P	-	S
	C min,ss	minimum plasma concentration at steady state	-	S	-	-
	C av,ss	average plasma concentration at steady state	-	S	-	-
	t max	time to reach maximum plasma concentration	S	S	S	S
	t 1/2	terminal elimination half-life	S	S	S	S
	λ z	rate constant of elimination	S	S	S	S
	MRT	mean residence time	S	-	-	-
	CL/F	apparent total body clearance	S	-	-	-
	CL ss /F	apparent total body clearance at steady state	-	S	-	-
	Vz/F	apparent volume of distribution	S	S	-	-
	PTF	peak-trough fluctuation	-	S	-	-
	R AUC b	accumulation ratio calculated from AUC at steady state and AUC after single dose	S		-	-
	R max	accumulation ratio calculated from C max,ss and C max	S		-	-

a metabolites of BRV (ucb-42145, ucb-100406-1, and ucb107092-1)

b AUC0-12 on Day 1 will be derived for the calculation of RAUC.

P: Primary, S: Secondary.

#### PK parameters in plasma

- AUC parameters (AUC(0-t), AUC(0-12), AUC(0-12),ss, AUC) [ng·h/mL]
  - The linear up/log down trapezoidal method is used to calculate the AUC parameters.
  - AUC: Calculated as AUC(0-t)+Clast/λz
    - If the percentage of extrapolated AUC (AUCextr) is more than 20%, the individual result should be excluded from summary statistics along with all parameters dependent on AUC.
- Cmax parameters (Cmax, Cmax,ss) [ng/mL]
  - Obtained directly from the concentration vs. time data

- $C_{\min,ss}$  [ng/mL]
  - Obtained directly from the concentration vs. time data
- $C_{av,ss}$  [ng/mL]
  - Calculated as  $AUC_{(0-12),ss}/12$
- $t_{\max}$  [h]
  - Obtained directly from the concentration vs. time data as a time at which  $C_{\max}$  or  $C_{\max,ss}$  is observed.
- $\lambda_z$  [1/h]
  - Estimated at terminal phase by linear regression after natural log-transformation of the concentrations.  $\lambda_z$  is calculated over a time interval using the best fit method.
    - The time interval should be equal to at least  $2 \times t_{1/2}$  and have at least 3 data-points not including  $C_{\max}$ . If it is less than 2 half-lives or if there are too few data to calculate  $\lambda_z$ , then the parameter should be excluded from summary statistics (along with all parameters dependent on half-life).
    - In the case that the  $R^2$  for the regression is less than 0.8, the half-life (and all parameters dependent on it) should be excluded from summary statistics.
  - Calculated as  $\ln 2 / \lambda_z$ 
    - For the parameter, same notation as corresponding  $\lambda_z$  is noted in the listing if the  $\lambda_z$  has the above-mentioned notation.
- MRT [h]
  - Calculated after single dose as  $AUMC/AUC$ , where AUMC is the area under the first moment curve from 0 to infinite time
  - $AUMC = AUMC_{(0-t)} + C_{\text{last}} \times t_{\text{last}} / \lambda_z + C_{\text{last}} / \lambda_z^2$
  - $AUMC_{(0-t)} = \int_0^{t_{\text{last}}} C(t) \times t \, dt$
- CL/F [L/h]
  - Calculated as dose/AUC
- $CL_{ss}/F$  [L/h]
  - Calculated as dose/ $AUC_{(0-12),ss}$
- $V_z/F$  [L]
  - Calculated as  $CL/F/\lambda_z$
- PTF
  - Calculated as  $(C_{\max,ss} - C_{\min,ss})/C_{av,ss}$

This document cannot be used for marketing authorization applications and must not be distributed without the prior written consent of the European Medicines Agency.

- R (accumulation ratio) ( $R_{AUC}$ ,  $R_{max}$ )
  - $R_{AUC}$  is calculated as  $AUC_{(0-12),ss} / AUC_{(0-12)}$
  - $R_{max}$  is calculated as  $C_{max,ss} / C_{max}$

If any parameter matching an exclusion criterion is included in summary statistics, then the rationale will be provided.

For the determination of the PK parameters, all BLQ values occurring prior to  $C_{max}$  are replaced by 0, except for embedded BLQ values (between two measurable data-points) which are treated as missing. Post- $C_{max}$  BLQ values are treated as missing.

The PK parameters are summarized for the PK-PPS by dosing period using descriptive statistics: the number of values (n), geometric mean, lower and upper limit of the 95% CI for geometric mean, geometric CV [%], arithmetic mean, SD, median, minimum and maximum values. For  $t_{max}$ , only n, median, minimum and maximum values are be presented.

Descriptive statistics should be reported to 4 significant figures for the mean, median and SD, and to 3 significant figures for all others.

If at least two thirds of the participants have a PK parameter reported then descriptive statistics will be calculated, otherwise only minimum and maximum will be reported for this PK parameter and all other descriptive statistics will be reported as “NE” (not estimable).

Individual PK parameters of BRV and its metabolites are provided together in the summary table. Individual PK parameters will be reported to 3 significant figures. If a parameter cannot be calculated, it will be reported in the listing either as “NE” (in case calculation is not possible due to missing data) or as “NC” (not calculable, in case data were available but the calculation was considered unreliable). Individual PK parameters of BRV and its metabolites for participants excluded from the PK-PPS are listed for SS.

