**Table 1–2: Single-Dose Period: schedule for ECGs, vital signs, and PK sampling**

Assessment	Time relative to BRV administration															
			Postdose (h)													
	Day 1												Day 2			
	Predose	0.25	0.5	1	1.5	2	3	4	6	9	12	16	24	36	48	72
12-lead ECG	X a	--	--	X	--	X	--	X	--	--	--	--	--	--	--	X
Vital signs b	X	--	--	X	--	X	--	X	--	--	--	--	--	--	--	X
Blood samples for PK	X	X	X	X	X	X	X	X	X	X	X	X	X	X	X	X

BRV=brivaracetam; DBP=diastolic blood pressure; ECG=electrocardiogram; PK=pharmacokinetics; SBP=systolic blood pressure  
 a. Three ECGs to be performed at 15min ( $\pm$ 5min) intervals within 24h prior to BRV dosing on Day 1 to provide a representative baseline  
 b. Vital sign assessments include SBP, DBP, pulse rate, respiratory rate, and body temperature.

In the Multiple-Dose Period, participants will receive BRV 200mg/day (100mg every 12h  $\pm$ 15min). Participants will receive BRV under fasting conditions with 200mL water. Blood samples will be taken for the determination of the PK profile of BRV and its metabolites (ucb-42145, ucb-100406-1, and ucb107092-1) predose prior to the morning dose administration on Day 5 to Day 9, and at predosing and at the following time points after the last administration of the IMP on Day 10: 0.25, 0.5, 1, 1.5, 2, 3, 4, 6, 9, 12, 16, 24, 36, 48, and 72h (Table 1–3).

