##### **5.1.1.1.3 Study periods and visits**

The following study periods/visits are defined for the classification by study period/visits:

- Screening Visit: Day -28 to Day -2
- Treatment Period: Day -1 to Day 13 (14 in-house days)
- Single-Dose Period: Day -1 to Day 4
- Multiple-Dose Period: Day 5 to Day 13
- SFU Visit: Day 15 (2 days after discharge)

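### Do the missing multiple-dose Vz/F formula and the unstated interval for Cmin,ss in SAP 5.7.1.1 put these secondary parameters at risk?

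*SAP*

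**What the plan says.** Protocol 4.2 and SAP Table 5-4 list Vz/F, Cmin,ss and PTF of brivaracetam as secondary multiple-dose parameters. Protocol 12.3.1 leaves the calculation methods to the SAP.

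**Vz/F.** Under PK parameters in plasma, SAP 5.7.1.1 gives one formula, CL/F divided by λz, without naming a period. CL/F is dose/AUC, with AUC taken to infinity. Table 5-4 plans Vz/F in both periods but AUC and CL/F for single dose only. For multiple dose it plans CLss/F, the "apparent total body clearance at steady state", defined as dose/AUC(0-12),ss.

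**Cmin,ss and PTF.** Table 5-4 describes Cmin,ss as the "minimum plasma concentration at steady state". The method is only "Obtained directly from the concentration vs. time data". PTF is (Cmax,ss − Cmin,ss)/Cav,ss, and Cav,ss is AUC(0-12),ss/12. Parameters "are calculated from the individual drug concentration vs. actual time profiles by dosing period". SAP 5.1.1.1.3 sets the "Multiple-Dose Period: Day 5 to Day 13". Samples in that period are taken "predose prior to the morning dose administration on Day 5 to Day 9", then before the Day 10 dose and up to 72 h after it.

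**The concern.** For Vz/F, the only written formula uses a clearance that the plan does not derive for the multiple-dose period. The MRT bullet is expressly restricted ("Calculated after single dose as") and the Vz/F bullet is not, so someone might apply dose/AUC to infinity to the Day 10 profile. After the last of many doses, that area includes drug left from earlier doses, so clearance and volume would come out too low.

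For Cmin,ss, the multiple-dose period contains more than one dosing interval. The lowest value anywhere in it is not a trough: it is either the Day 5 predose sample or a late washout sample. PTF would inherit that value. Cmax,ss has the same wording, but its maximum falls within the dosing interval anyway, so the missing bound matters only for a minimum.

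At stake would be three secondary multiple-dose parameters that could differ materially between analysts.

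**Working it through.** The documents give no figure to reproduce here. The check sizes the misreadings and then asks whether the plan permits them.

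**Inputs.** From the documents: half-life about 9 h and linear kinetics (protocol 5.3); one dose on Day 1, then 11 doses every 12 h from Day 5 to the morning of Day 10; the planned sampling times. Assumed: one compartment, absorption rate 1 to 5 per hour, all samples quantifiable. The half-life was also varied from 7 to 11 h.

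**Vz/F**

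1. k = ln 2/9 = 0.0770 per hour, and exp(−12k) = 0.397.
2. Ignoring absorption, AUC to infinity after the last dose divided by AUC(0-12),ss is 1/(1 − 0.397) = 1.66. With absorption it is 1.67-1.71.
3. A Day 10 dose/AUC to infinity would therefore give 0.58-0.60 of the true volume, or 40-42% too low (0.51-0.69 of it for half-lives of 7 to 11 h).
4. That reading needs two quantities that Table 5-4 marks as not derived for multiple dose. The table leaves two candidates:
   - (CLss/F)/λz = dose/(AUC(0-12),ss × λz): ratio to the true volume 1.00.
   - (single-dose CL/F)/λz: under linear kinetics single-dose AUC to infinity equals AUC(0-12),ss, so the ratio is again 1.00.
5. The contrast with MRT carries little weight. The AUC and CL/F bullets name no period either, yet Table 5-4 limits both to single dose for brivaracetam. The table assigns parameters to periods; the bullets do not.

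**Cmin,ss and PTF**

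1. The 0-12 h reading gives PTF 0.63-0.82. For example, at an absorption rate of 2 per hour Cmin,ss/Cmax,ss is 0.461 and PTF is 0.740, so Cmax,ss/Cav,ss = 0.740/(1 − 0.461) = 1.373.
2. If the minimum were taken over the Day 10 profile to 72 h: C72/C12 = 2^(−60/9) = 0.0098, about 1% of the trough, and PTF would be 1.28-1.43.
3. If it were taken over the whole of Day 5 to Day 13, the lowest value would be the Day 5 predose sample, 96 h after the single dose. Relative to the trough it is 2^(−96/9) ÷ [0.397/(1 − 0.397)] = 0.000615/0.658 = 0.0009, about 0.09%. If below quantification it precedes Cmax and is set to 0. In the example PTF would then be about 1.37.
4. On the Day 10 profile, later "BLQ values are treated as missing", so an unquantifiable 72 h value would only move the minimum to an earlier washout sample.
5. None of these samples is at steady state. Day 5 predose comes before the first multiple dose, and samples from 16 h onward follow an evening dose that is not given on Day 10. The Day 10 predose and 12 h samples are the troughs of the interval over which AUC(0-12),ss and Cav,ss are computed.

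**The case for a change.** The strongest case for a change is that the protocol hands the methods to the SAP, so they should be written there. The authors did settle similar questions elsewhere: a footnote to Table 5-4 fixes the single-dose area used in RAUC. Where they want analyst judgement, as for a missing multiple-dose predose value, they say so and require a recorded rationale. For Vz/F and Cmin,ss they do neither. Using single-dose CL/F for the multiple-dose volume would give the right size, but it would not be an independent Day 10 estimate. The sponsor's non-compartmental data handling rules may fill the gap, but the SAP's version history mentions them only for plotting values below quantification, and they are not available here.

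It stands that the text is incomplete, and a line for each parameter would make it self-contained at almost no cost. It does not stand that analysts following the plan would report clearly different values. For Vz/F, the readings that fit Table 5-4 agree under the stated linear kinetics. For Cmin,ss, the divergent readings require ignoring the steady-state label, the peak-trough meaning of PTF and its 0-12 h denominator. The unseen sponsor rules are not needed for this conclusion.

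**Conclusion.** The omission is real but does not call for a change. Followed as written, with Table 5-4 read alongside the formulas, the plan leads to a multiple-dose Vz/F with a ratio of 1.00 to the true value and to a Cmin,ss from the Day 10 dosing interval, with PTF of about 0.63-0.82 in the illustration. The 40-42% shortfall in Vz/F and the PTF of 1.28-1.43 measure misreadings; they are not expected results.

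This rests on linear kinetics, which the documents state, and on an analyst giving the words at steady state their usual meaning. The exact figures also depend on the one-compartment model and the assumed absorption rates; the choice between readings does not.

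The consequences of a slip would be limited. The parameters are secondary and descriptive in a 12-subject, single-arm study with no hypothesis test. AUC(0-12),ss and Cmax,ss are untouched. Individual concentrations are listed with actual times, so a wrong value could be found and recomputed. Writing out both definitions would be tidy, but it would not alter a result obtained by following the plan.

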### **5.7.1.2 Pharmacodynamics**

Not applicable.

### **5.7.1.3 Genomics**

Not applicable.

## **5.8 Subgroup analyses**

Not applicable.

## **5.9 Interim Analyses**

Not applicable.

## 5.10 Data Monitoring Committee (DMC) or Other Review Board

Not applicable.

# 6 SUPPORTING DOCUMENTATION

## 6.1 Appendix 1 Non-key analysis specifications

### 6.1.1 Baseline characteristics and demographics

Unless otherwise specified, demographic and Baseline characteristics are summarized for the SS, and subject data listings for the demographic and Baseline characteristics are provided for the All Subject Screened (ES).

#### Demographics

Age, gender (male/female), weight (kg), height (cm), body mass index (BMI), ethnicity, and racial group (Asian) are summarized.

The age of each subject is calculated as completed years at the date of informed consent. Weight is summarized from screening visit. BMI is calculated from the weight and the height at screening visit using the following formula:

$$\text{BMI}(\text{kg}/\text{m}^2) = \frac{10,000 \times \text{weight} (\text{kg})}{[\text{height} (\text{cm})]^2}$$

#### Other Baseline characteristics

Lifestyle information will be summarized based on the SS and will be listed based on the ES.

Serology, urine drug, and alcohol detection will be listed based on ES. The detailed tests of serology and urine drug are listed below:

- Serology

Hepatitis B surface antigen, Hepatitis C virus antibody, HIV antibody, and syphilis

- Urine drug

Morphine, Tetrahydrocannabinolic acid, Methamphetamine, Dimethylenedioxymethamphetamine, Ketamine, and Cocaine

### 6.1.2 Protocol deviations

The number and percentage of participants with at least 1 IPD are summarized for SS, using the categories as defined in the protocol deviation specification.

A listing of all IPDs identified at the DEM will be presented based on the SS and will include the deviation type and description.

### **Impact of COVID-19 on study visits**

The number and percentage of participants with visits impacted by COVID-19 will be summarized by impact categories based on the SS. And a listing of visits impacted by COVID-19 will be presented for all participants based on the ES, including visit, visit date, relative day, impact category, relationship to COVID-19 and narrative of the event.

### **6.1.3 Medical history**

#### **Medical history**

The number and percentage of participants with a medical history condition, including both resolved previously and ongoing conditions at the time of study entry, are summarized overall (ie, any previous and ongoing medical history conditions) and by MedDRA primary SOC and PT.

A subject data listing for the previous and ongoing medical history conditions is provided.

